2.3 Treatment Assignment and Blinding

Subjects will remain on a stable dose of MTX until Week 24 (unless qualifying for rescue therapy as described in Protocol Section 5.4); thereafter MTX may be adjusted within the range of 7.5 – 25 mg/week. At Baseline, approximately 425 subjects will be randomized to 5 treatment groups in a 1:1:1:1:1 ratio to receive ABBV-154: 40 mg, 150 mg, 340 mg SC EOW; 340 mg SC E4W, or placebo. Randomization will be stratified by Baseline glucocorticoid (yes/no); number of prior failed b/tsDMARDs (1; 2 or more); and prior anti-TNF failure (yes/no) and if yes further stratification by prior adalimumab use (yes/no). At Week 12, subjects assigned to placebo will be re-randomized in a 1:1 ratio to receive ABBV-154 150 mg or 340 mg SC EOW; subjects from the other dose groups will continue with their respective dose and dosing regimen. Re-randomization will be stratified by Baseline glucocorticoid use (yes/no) and prior adalimumab use (yes/no). The

enrollment for subjects with prior adalimumab use is capped at approximately 30% of the total subjects enrolled. Systemic glucocorticoids (dose of ≤ 7.5 mg/d prednisone equivalent at Baseline) must be tapered off within 4 weeks of the start of study drug.

All AbbVie personnel with direct oversight of the conduct and management of the trial (except for AbbVie Drug Supply Management Team) will be blinded to each subject's treatment through Week 12. The AbbVie study team will be unblinded to treatment assignment for the Primary Analysis. This unblinding will take place after all subjects have completed the Week 12 visit or have withdrawn from the study prior to Week 12. To maintain integrity of the trial, the study site personnel and the subjects will remain blinded until all subjects have either completed the last visit of LTE Period 1 or have withdrawn from the study. Blinded dosing regimens will be continued until the previous criteria are met. To maintain the blind, the ABBV-154 and placebo pre-filled syringes provided for the study will be identical in appearance. The IRT will provide access to unblinded subject treatment information in the case of a medical emergency.

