2.4 Sample Size Determination

The planned total sample size of 425 subjects (approximately 85 subjects per treatment group) provides at least 90% power to detect a 22% difference between ABBV-154 and placebo in ACR50 response rate at Week 12 (assuming a placebo ACR50 response rate of 13%), at a 2-sided significance level of 0.1 based on Chi-square test.

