- **Multiple Imputation (MI):** a sensitivity analysis for the primary endpoint: Markov Chain Monte Carlo (MCMC) will be first applied to augment data into monotonic missing pattern and PROC MI will be used to generate 30 datasets using the regression method. The variables to be included in the imputation model for the Placebo-Controlled Period are treatment group, stratification factors at randomization [Baseline glucocorticoid (yes/no), number of prior failed b/tsDMARDs (1; 2 or more), and a combined prior anti-TNF failure/adalimumab use factor (prior anti-TNF failure with adalimumab use; prior anti-TNF failure without adalimumab use; no prior anti-TNF failure)], Baseline, and measurements at each visit in the Placebo-Controlled Period. The variables to be included in the imputation model for the LTE periods are treatment group, major stratum [baseline glucocorticoid use (yes/no) and prior adalimumab use (yes/no)], Baseline, and measurements at each visit in the LTE periods. The random seed for MCMC and the random seed for PROC MI are specified in Appendix C. The imputed post-baseline measurements will be rounded to the same precision as the observed data before the determination of responder status. Subjects will be characterized as responders or non-responders based on the MI imputed datasets. Using the Cochran-Mantel-Haenszel (CMH) model adjusted by stratification factors [Baseline glucocorticoid (yes/no), number of prior failed b/tsDMARDs (1; 2 or more), and a combined prior anti-TNF failure/adalimumab use factor (prior anti-TNF failure with adalimumab use; prior anti-TNF failure without adalimumab use; no prior anti-TNF failure)], the imputed endpoints will be analyzed using each of the 30 datasets. SAS PROC MIANALYZE will be used to generate the

final inferences of the risk difference between each ABBV-154 group and placebo.

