Appendix C. Random Seeds

In case of non-convergence, the random seed will be updated by adding 10000 at each attempt until convergence of model happens.

A. Random Seeds for NRI-MI

Endpoints	Random Seed	
	MCMC procedure	PROC MI
TJC68	10001	20001
SJC66	10002	20002
TJC28	10003	20003
SJC28	10004	20004
Patient's Assessment of Pain	10005	20005
Patient's Global Assessment of Disease Activity	10006	20006
Physician's Global Assessment of Disease Activity	10007	20007
HAQ-DI	10008	20008
hsCRP	10009	20009

B. Random Seeds for MI

Endpoints	Random Seed	
	MCMC procedure	PROC MI
TJC68	40001	50001
SJC66	40002	50002
Patient's Assessment of Pain	40005	50005
Patient's Global Assessment of Disease Activity	40006	50006
Physician's Global Assessment of Disease Activity	40007	50007
HAQ-DI	40008	50008
hsCRP	40009	50009

final inferences of the risk difference between each ABBV-154 group and placebo.

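### The SAP implies that ACR components are imputed in separate runs, which understates ACR50 among imputed subjects, with little effect on the treatment difference

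*SAP*

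**What the plan says.** SAP 9.2.2 makes NRI-MI the primary approach for categorical endpoints. A subject without an evaluation in the visit window is a non-responder, with two exceptions. A subject who responded both before and after the window is a responder. Data missing because of COVID-19 or logistical/geo-political problems go to multiple imputation. SAP 9.3.3 adds multiple imputation of missing data in general as a sensitivity analysis of the primary endpoint.

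Only one imputation model is described, in 9.2.2. MCMC first produces a monotone pattern; then "PROC MI will be used to generate 30 datasets using the regression method". For the placebo-controlled period the model contains treatment group, the stratification factors, "Baseline, and measurements at each visit in the Placebo-Controlled Period". No other component is listed as a predictor. Responder status is determined after the imputed measurements have been rounded.

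Appendix C is the main evidence for separate runs. Its first table, "Random Seeds for NRI-MI", gives each of nine measures its own MCMC seed and its own PROC MI seed, with TJC28 and SJC28 listed apart from TJC68 and SJC66. The second table, for the MI sensitivity analysis, does the same for the seven ACR components (TJC68 has 40001 and 50001, hsCRP has 40009 and 50009).

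Under SAP 9.3.1 an ACR50 responder needs at least 50% improvement in TJC68, in SJC66 and in at least three of five further measures.

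**The concern.** A joint model would need one seed pair. A pair for each measure, with a variable list that names no other component, describes one run per measure, whose results are put together afterwards. Each run draws its residuals without knowledge of the others. ACR50 depends on the joint distribution of seven measures in one subject, so if the draws are less correlated than real data, simultaneous success is too rare.

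Two analyses of the primary endpoint are touched. In the primary NRI-MI analysis, the SAP treats COVID-19 and logistical missingness as missing at random and therefore imputes it; separate runs partly undo that choice. The MI analysis is the only alternative missing-data method named for the primary endpoint, and it imputes more subjects. The primary response rates also feed the MCP-Mod analysis in SAP 9.6. The binary DAS28 and CDAI endpoints under NRI-MI combine components seeded in the same separate way.

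**Working it through.** **1. The plan's own figure.** SAP 2.4 states that the sample "provides at least 90% power to detect a 22% difference between ABBV-154 and placebo in ACR50 response rate at Week 12", "at a 2-sided significance level of 0.1 based on Chi-square test". Inputs: 85 per arm, 13% against 35%.

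- Pooled rate 0.24. SE under the null = √(2 × 0.24 × 0.76 / 85) = 0.0655.
- SE under the alternative = √((0.13 × 0.87 + 0.35 × 0.65) / 85) = 0.0633.
- Power = Φ((0.22 − 1.645 × 0.0655) / 0.0633) = Φ(1.77) = 96.2%.

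The statement of at least 90% is reproduced.

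**2. Model for the imputed subjects.** The documents give no figure here, so these are assumptions. Seven normal improvement scores have a common correlation ρ within a subject and a common success probability q, chosen so that true ACR50 is 13% or 35%. R² is the share of a component's Week 12 variance explained by its own earlier visits. The correlation is taken to be the same in the explained and the residual part. Separate runs keep the correlation in the explained part and draw the residuals independently, so ρ falls to ρ × R².

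**3. ACR50 among imputed subjects under separate runs** (400,000 simulated subjects):

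| ρ | True rate | R² = 0 | R² = 0.5 | R² = 0.75 |
|---|---|---|---|---|
| 0.3 | 13% | 5.0% | 9.1% | 11.1% |
| 0.3 | 35% | 26.8% | 31.1% | 33.1% |
| 0.5 | 13% | 2.3% | 7.4% | 10.2% |
| 0.5 | 35% | 20.7% | 28.4% | 31.7% |
| 0.7 | 13% | 0.9% | 6.0% | 9.2% |
| 0.7 | 35% | 14.4% | 25.2% | 30.0% |

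**4. Hand check of the R² = 0 column.** With independent components, ACR50 = q² × P(Binomial(5, q) ≥ 3).

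- ρ = 0.5, true 13%: q = 0.332, giving 0.1102 × 0.2079 = 2.3%.
- ρ = 0.5, true 35%: q = 0.572, giving 0.3272 × 0.6331 = 20.7%.

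**5. Check with actual imputation.** Bayesian regression imputation was run on 600 simulated trials of 5 × 85 subjects, with ρ = 0.5, 10% missing at Week 12 and 10 imputations.

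| Setting | Arm | True | Separate | Joint |
|---|---|---|---|---|
| Earlier visits observed (R² about 0.5) | Placebo | 12.8% | 7.5% | 13.4% |
| Earlier visits observed (R² about 0.5) | Active | 35.8% | 28.2% | 35.0% |
| No earlier post-baseline visit | Placebo | 12.6% | 2.6% | 13.3% |
| No earlier post-baseline visit | Active | 35.3% | 20.9% | 35.0% |

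Separate runs agree with step 3. Joint imputation comes within 0.8 point of the true rate.

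**6. Whole-arm effect.** Arm rate = (1 − f) × true rate + f × rate among imputed subjects, with f = 10% assumed.

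- Central case (ρ 0.5, R² 0.5): placebo 0.9 × 13 + 0.1 × 7.4 = 12.4%; active 0.9 × 35 + 0.1 × 28.4 = 34.3%; difference 21.9 points.
- Worst case (ρ 0.7, R² 0): placebo 0.9 × 13 + 0.1 × 0.9 = 11.8%; active 0.9 × 35 + 0.1 × 14.4 = 32.9%; difference about 21.2 points, power 95.7%.

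With 2% or 5% imputed, the central difference is 21.98 or 21.95 points. Over the whole grid (f 2 to 10%, R² 0 to 0.75), power lies between 95.7% and 96.5%.

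**7. Comparison with non-response.** If the same 10% were all set to non-response in both arms, the difference would be 0.9 × 22 = 19.8 points, against 21.2 to 22.0 under separate imputation.

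**The case against.** The best case against the point has three parts.

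First, no sentence in the SAP says that components are imputed one at a time. That is true: it is an inference from the variable list and the seeds. But nothing in either document points to joint imputation, and per-measure seed pairs have no natural use in a single run. If joint imputation is intended, the text still needs correcting.

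Second, the damage is small. Both arms are biased downward and no scenario in the grid enlarges the treatment difference. The primary analysis imputes only a subset of missing data. This stands, and it sets the weight of the point.

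Third, a subject's history protects the correlation. Protocol Appendix E collects all seven components at Baseline, Day 4 and Weeks 2, 4, 8 and 12, so a missed Week 12 visit usually leaves earlier values. This also stands; the R² = 0 column is an extreme.

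Stronger readings are tempting but not supported. A reader might infer that the correlation is broken altogether; that holds only where no earlier post-baseline visit is observed. A reader might infer that the MI sensitivity analysis collapses into non-responder imputation and tests nothing. It is pulled partly that way, but step 7 shows a clear contrast. A reader might extend the point to all DAS28 and CDAI endpoints. The continuous ones are analysed by MMRM (SAP 9.2.3, 9.4.2) and are unaffected.

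**Conclusion.** The point holds for imputed subjects. Read naturally, SAP 9.2.2 and Appendix C describe separate runs, and these understate ACR50 in every scenario examined: about 1 to 11% where the truth is 13%, and about 14 to 33% where it is 35%. The bias is not a threat to the trial's conclusion. With 10% imputed, the difference loses about 0.1 point in the central case and about 0.8 in the worst, and the sample-size statement is untouched. The MI sensitivity analysis carries more of the bias than NRI-MI because it imputes missing data of all kinds.

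These sizes rest on assumed values for ρ, R² and the fraction imputed, and on normal, equally correlated components. For the binary DAS28 and CDAI endpoints, which are thresholds on composite scores, neither size nor direction was tested. The case for a change is that a better method is available cheaply.

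**What to change.** In SAP 9.2.2 and Appendix C, impute all ACR components at all visits in one run with one seed pair for each of NRI-MI and MI. MCMC to a monotone pattern followed by the regression method still works if the variables are ordered visit by visit, so that each component conditions on the others at the same visit; fully conditional specification is an alternative. Derive ACR20, ACR50 and ACR70 afterwards. Treat the components of the binary DAS28 and CDAI endpoints in the same way.

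The cost is SAP wording and some programming; design, sample size and data collection do not change. The drawback is a larger model. If it does not converge, the predictors can be reduced to the other components at the same and the previous visit, and the SAP should name that fallback in advance.

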9.2 Handling of Intercurrent Event and Missing Data

9.2.1 Missing Data due to COVID-19 and Logistical Problems (Geo-political Restrictions)

Missing data could occur due to various reasons, including missing visits/assessments, early withdrawal from the study, or missing due to COVID-19 infection or logistic restriction, as well as due to logistical problems (geo-political restrictions).

The COVID-19 pandemic is interfering with the conduct of many ongoing trials, with potential impacts on treatment duration and the collection, analysis, and the interpretation of clinical trial data. Some protocol-specified visits in the clinical trials may be impacted due to COVID-19 infection or logistical restrictions during the pandemic. Impacted visits due to COVID-19 will be recorded in the database. The probability of having missed visits and missing data due to COVID-19 infection or logistical restrictions related to the COVID-19 pandemic can be reasonably assumed to be unrelated to the unobserved values. Therefore, for the purpose of statistical analysis, it is reasonable to assume that these missing data are missing at random (MAR) and the statistical models that require MAR assumption are appropriate. Sensitivity analyses will be performed to assess the impact of missing data and the robustness of the conclusion. The same logic is likely applicable to data missing due to logistical problems (geo-political restrictions) so that the MAR assumptions is also applicable.

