9.2.2 Handling of missing data in Categorical Endpoints

- Non-Responder Imputation incorporating multiple imputation to handle COVID-19 and logistical problems (geo-political restrictions) (NRI-MI) will be the primary approach to handle missing data for categorical endpoints. The

NRI-MI will categorize any subject who does not have an evaluation during a pre-specified visit window (either due to missing assessment or due to early withdrawal from the study) as a non-responder for the visit. The only exceptions are: 1) when the subject is a responder both before and after the visit window, where the subject will be categorized as a responder for the visit, and 2) when the data is missing due to COVID-19 infection or logistical restriction, or logistical problems (geo-political restrictions), which will then be handled by Multiple Imputation. Subjects whose change/percent change from Baseline cannot be calculated because of a missing Baseline will be considered as a non-responder at all post-baseline visits in NRI-MI approach.

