9.5 Additional Efficacy Analyses

The primary and all secondary efficacy variables will be analyzed at all visits assessed other than Week 12, including in the LTE periods, using methods mentioned above. At time of the Primary Analysis, NRI will be used after Week 12 for all binary endpoints.

In addition, other efficacy endpoints described in Section 3.3 will be analyzed at all visits assessed using the same methods as secondary endpoints.

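### The long-term extension imputation model leaves out all Placebo-Controlled visits, so for subjects lost to COVID-19 or geo-political causes soon after Week 12 it ignores their Week 12 data

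*SAP*

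**What the plan says.** SAP 9.2.2 gives two lists of imputation variables. For the Placebo-Controlled Period the list ends with "Baseline, and measurements at each visit in the Placebo-Controlled Period". For the extension it reads "The variables to be included in the imputation model for the LTE periods are treatment group, major stratum" (baseline glucocorticoid use and prior adalimumab use), then "Baseline, and measurements at each visit in the LTE periods". The number of prior failed b/tsDMARDs is in the first list but not the second.

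The same section fixes where imputation is used. Under NRI-MI a subject with no evaluation in the visit window is counted, "either due to missing assessment or due to early withdrawal from the study) as a non-responder for the visit". One exception is a subject who responds both before and after the window. The other is "when the data is missing due to COVID-19 infection or logistical restriction, or logistical problems (geo-political restrictions), which will then be handled by Multiple Imputation". Full multiple imputation is introduced as "a sensitivity analysis for the primary endpoint", which is ACR50 at Week 12.

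SAP 9.2.4 summarizes long-term efficacy As Observed by treatment sequence, and adds NRI-MI for selected categorical variables. SAP 9.5 analyses the primary and secondary variables at other visits, "including in the LTE periods, using methods mentioned above", but specifies plain NRI for binary endpoints after Week 12 at the time of the Primary Analysis. SAP 9.2.1 justifies missing at random by stating that COVID-19 missingness "can be reasonably assumed to be unrelated to the unobserved values", and says the same reasoning is likely to apply to geo-political loss.

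**The concern.** Week 12 closes the Placebo-Controlled Period, and the next joint counts are at Week 14. For an early LTE visit, Week 12 is likely to be the best single predictor available, and it has already been collected. A geo-political interruption can remove every later visit. SAP version 2.0 added this cause to NRI-MI, and the country list in the Protocol synopsis includes Russia and Ukraine. A subject lost in this way just after Week 12 has no LTE value. The model then knows the treatment group, two stratum factors and the Baseline value, but not whether the subject was responding at Week 12.

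Two things are at stake. The imputations are noisier than they need be. Missing at random also has to hold without conditioning on Week 12 status, which is harder to defend than the same assumption with it. NRI-MI is not consistent with itself here either: its before-and-after exception would naturally take Week 12 as the earlier visit when Week 14 is missed, while its imputation step ignores Week 12.

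**Working it through.** **The plan's own figure.** SAP 2.4 states at least 90% power with 85 per group, 13% against 35% (13% + 22%), two-sided alpha 0.1. With a pooled rate of 0.24:

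- null SE = sqrt(2 × 0.24 × 0.76 / 85) = 0.0655
- alternative SE = sqrt((0.13 × 0.87 + 0.35 × 0.65) / 85) = 0.0633
- power = Φ((0.22 − 1.645 × 0.0655) / 0.0633) = 96.2%

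The statement is reproduced and does not depend on the LTE imputation model.

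**Inputs for the illustration.** The active rate of 35% comes from SAP 2.4 and is carried to the LTE visit as an assumption. Also assumed, because the documents give no values: a Week 12 to LTE correlation of 0.4 to 0.9; a fraction f of the arm handled by imputation of 2%, 5% or 10% (1.7, 4.25 or 8.5 subjects of 85); and no observed LTE visit for any of them.

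**Missingness unrelated to response.** Baseline, Week 12 and LTE scores were simulated as multivariate normal (400,000 subjects, Baseline correlation 0.3, f = 10%) and the LTE score imputed by regression. At correlations 0.5 / 0.7 / 0.85 the true arm rates were 34.8 / 34.9 / 35.0%, and the listed model gave 34.8 / 34.9 / 35.0%. There is no bias.

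Information is still lost. With Baseline only, explained variance is 0.3² = 9%. With Week 12 added it is (0.3² + r² − 2 × 0.3 × 0.3 × r) / (1 − 0.3²), which is 27%, 50% and 72% at r = 0.5, 0.7 and 0.85.

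**Worst case: every imputed subject is a Week 12 non-responder.** Let c be the 65th percentile of the standard normal and q the LTE response probability given Week 12 non-response:

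- q = (0.65 − Φ₂(c, c; r)) / 0.65
- if the missing subjects are imputed at the observed-arm mean, the arm rate becomes (0.35 − f·q) / (1 − f)
- overstatement = f(0.35 − q) / (1 − f)

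| r | q | f = 2% | f = 5% | f = 10% |
|---|---|---|---|---|
| 0.4 | 26.1% | 0.18 | 0.47 | 0.99 |
| 0.5 | 23.6% | 0.23 | 0.60 | 1.26 |
| 0.6 | 21.0% | 0.29 | 0.74 | 1.56 |
| 0.7 | 18.0% | 0.35 | 0.89 | 1.89 |
| 0.8 | 14.6% | 0.42 | 1.07 | 2.27 |
| 0.9 | 10.2% | 0.51 | 1.30 | 2.75 |

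Overstatement is in percentage points. Example: r = 0.7, f = 10% gives 0.10 × 0.170 / 0.90 = 1.89.

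The simulation of the same worst case at f = 10%, with Baseline in the model, gave 1.0, 1.6 and 2.2 points at r = 0.5, 0.7 and 0.85. These are somewhat smaller, in part because Baseline carries some information. The listed model imputed 34-35% response where the true rate was 24%, 18% and 13%. Adding Week 12 brought the arm rate to 34.9%, 35.0% and 35.0% against true values of 34.9%, 35.0% and 35.0%.

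**Scale.** The standard error of a 35% rate in 85 subjects is sqrt(0.35 × 0.65 / 85) = 5.2 points, so even the extreme cell of the table is about half a standard error.

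**The case against.** A reader might infer that subjects who fail early and drop out are given average response rates in the LTE. The documents do not support this. NRI-MI sets an ordinary withdrawal to non-responder, so a subject who leaves for poor response contributes zero. The general reference in SAP 9.5 to methods already mentioned could be read as extending full multiple imputation to the LTE. However, SAP 9.2.2 and 9.3.3 tie full imputation to the primary endpoint, and SAP 9.2.4 names only As Observed, NRI-MI and MMRM for long-term efficacy.

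A reader might also say that imputation rests on Baseline alone. That is too strong: treatment group, the two stratum factors and every observed LTE visit are in the model. Baseline is the only clinical measurement used only when no LTE visit was observed.

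Three further arguments carry weight:

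- Under the SAP's own assumption about this missingness there is no bias. This stands, and it limits the point mainly to precision and robustness.
- The direction of bias is not fixed. If affected subjects or sites respond better than average, the listed model understates response, and Week 12 would recover only part of a site effect.
- Placebo subjects start ABBV-154 at Week 12, so their Week 12 non-response is not failure on ABBV-154. A common Week 12 slope could mis-specify their imputation. This is a sound objection to adding Week 12 naively, and the fix has to deal with it.

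The stakes are also low: there is no placebo arm after Week 12, and the main LTE summaries are As Observed.

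**Conclusion.** The omission is real as the list is written, though the SAP does not say outright whether Week 12, the boundary visit, counts as an LTE measurement. Its effect is confined to NRI-MI summaries of selected categorical variables in the LTE, and within those to data missing through COVID-19 or geo-political/logistical causes. The Week 12 primary analysis, its multiple-imputation sensitivity analysis, the As Observed summaries and the NRI used after Week 12 at the Primary Analysis are untouched.

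The certain cost is discarded information for subjects with no LTE value. Bias is about zero if the missingness is unrelated to response. The overstatement reaches the tabulated 0.2-0.5, 0.5-1.3 and 1.0-2.8 points (at 2%, 5% and 10% missing) only if all such subjects were Week 12 non-responders, under the assumed correlations. This is a minor improvement to a stated method and does not threaten the trial's main conclusions.

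**What to change.** In SAP 9.2.2, define the LTE imputation model as: treatment sequence (the six sequences of SAP 9.2.4), the stratification factors including number of prior failed b/tsDMARDs, Baseline, measurements at each Placebo-Controlled visit, and measurements at each LTE visit. Because placebo subjects change treatment at Week 12, let the Week 12 slope differ for the two re-randomized sequences, or impute those sequences separately. If the intention was already to include Week 12, say so.

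The cost is a sentence of SAP text and a longer variable list, with no new data. The drawback is some convergence risk, since the list already carries about 25 LTE visits per component. Separate imputation of the re-randomized sequences would be thin, at about 85 / 2 ≈ 42 subjects each. SAP Appendix C answers non-convergence only by changing the seed, so a reduced list that keeps at least Week 12 should be named in advance.
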